4.1 Inclusion Criteria

Participant responses to study measures will be evaluated by research staff to ensure all eligibility criteria are met before participants are enrolled into the full RCT. Participants will complete a brief eligibility screening survey to ascertain appropriateness for the study. Any questions pertaining to participant responses will be clarified with the participant prior to the determination of eligibility status. The ability to understand study procedures and to comply with them for the entire length of the study will be assessed prior to enrollment in the trial.

Inclusion criteria for the main RCT trial are:

- (a) at least legal adult age to consent without a guardian ((18 years of age or older in all states except Alabama (requires 19 years of age), Nebraska (requires 19 years of age), and Mississippi (requires 21 years of age))
- (b) having a diagnosis of an OUD within the past 12 months;
- (c) started buprenorphine (*the term we use to refer to all buprenorphine products including buprenorphine/naloxone*) treatment within the past 6 months
- (d) at least moderate or greater self-reported pain on average over the past 3 months;
- (e) regular and consistent access to a telephone and willingness to use the phone for study telephone sessions.

Participants in this study will be of legal adult age to consent without a guardian (18 years old or older in most states unless in Alabama (requires 19 years of age), Nebraska (requires 19 years of age) and Mississippi (requires 21 years of age) for several reasons. All participants will be patients prescribed buprenorphine for the treatment of an OUD who also experience pain. Due to the differences in pain management and intervention strategies for those 17 and younger relative to older individuals, a separate study would be required to appropriately examine opioid safety among children and adolescents age 17 and under with pain. Individuals age 18 to 20 will be included in the study because individuals in this age range receive medical care services related to OUD and pain in the same manner as those individuals age 21 and older.

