9.5.2 Secondary Outcomes

The **secondary outcomes** of interest are pain level, pain-related functioning, and frequency of substance use. We hypothesize that participants receiving the PPMI condition (intervention condition) will report less pain, an increase in pain-related functioning, and lower frequency of substance use over the 3-month (Secondary Aim 2) and 12-month (Secondary Aim 3) follow-up period when compared to the EUC condition (control condition).

These outcomes for both **Secondary Aims 2 and 3** will be measured in the following ways:

- **Pain level** will be measured using the Numerical Rating Scale for Pain Intensity (NRS-I), which will be collected at all time-points. For each follow-up time point, we will subtract the baseline value to obtain a change score. For this study, a clinically significant change in pain level will be operationalized as a 30% reduction of pain, which would equate to change of 2 points on a 0 to 11 pain intensity numerical scale such as the NRS-I.
- **Pain-related functioning** will be measured using the pain interference subscale of the Brief Pain Inventory – Short Form (BPI). The BPI Short Form is a widely used, validated measure that assesses both pain level and the impact pain has on functioning over the past 24 hours. For each follow-up time point, we will subtract the baseline value to

obtain a change score. For this study, an increase in pain-related functioning will be operationalized as a reduction in the pain interference scale scores over time.

- **Frequency of substance use** will be measured using the TLFB, which will be collected at all follow-up time-points. During this administration, the participant will be asked to recall their alcohol and drug use since the previous follow-up time point. Percent days abstinent from alcohol and drugs will be used as the primary measure of substance use at each assessment time point (baseline, 1-, 3-, 6-, 9-, and 12-month follow-up assessment).

To accomplish **Secondary Aim 4** (qualitative interviews for rapid implementation), a random sample (n=20) of participants who completed the PPMI condition will be interviewed in addition to a sample (n=15) of buprenorphine providers/clinic staff.

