means and standard deviations for these outcomes at baseline, 1-, 3-, 6-, 9-, and 12-months, as well as change scores from baseline for the two groups. We hypothesize that participants randomized to the PPMI will have less pain, better functioning, and lower frequency of opioid use at follow-ups compared to EUC. These secondary outcomes are hypothesized to meet the assumptions of continuous variables, and we will consequently use t-tests to make comparisons. If, however, the distribution of a given outcome measure is skewed, alternative modeling strategies will be used. We will use a linear mixed-effects model and estimate the treatment effect as the difference in the time-averaged changes from baseline in pain levels (using the NRS-I) and in pain-related functioning (using the BPI) over the course of follow-up (namely, at 3-months for secondary aim 2 and at 12-months for secondary aim 3). Because reduction in pain is of key interest, the analysis will model change-scores from baseline in the response variable as the dependent variable, and the independent variables will include the baseline values of the response variable, time in months since randomization and the treatment group indicator. The parameter estimate of the treatment group indicator will estimate the time-averaged treatment effect. If the graphical exploration (described above) shows potentially differential linear decrease in pain over time, we will include an interaction of time by treatment group indicator to model and test for this. For frequency of substance use, we will first assess the distribution of measures collected to assess alcohol use, illicit drug use and prescription opioid medication use to determine whether a summary or composite measure of each of these may represent the use or misuse more appropriately. For example, illicit drug use will be obtained as the number of days the participant used each of multiple drugs, and thus we may consider combining the days of any of the illicit drug use. We will also combine the alcohol and drug use data obtained using TLFB interviews as the percent days abstinent from alcohol and drugs during the past 30 days at each assessment time. We will then check the distribution of the substance use and prescription medication misuse (measured using the TLFB), and unless the data are highly skewed, we will use a linear mixed-effect model to test the hypothesis and to estimate the treatment effect as the difference in the time-averaged changes from baseline in these outcome measures over the course of the 12-month follow-up period.

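### Section 9.6 states baseline adjustment for the pain and functioning model but not for the substance-use model; adding baseline percent days abstinent is a nearly free gain in precision.

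*Combined protocol and SAP*

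**What the plan says.** Section 9.6 (Secondary Aims 2 and 3) describes two linear mixed models.

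- **Pain (NRS-I) and functioning (BPI).** The text gives a dependent variable: "Because reduction in pain is of key interest, the analysis will model change-scores from baseline in the response variable as the dependent variable". It also gives a covariate list: "the independent variables will include the baseline values of the response variable, time in months since randomization and the treatment group indicator".
- **Substance use.** The text then turns to substance use and starts again: "unless the data are highly skewed, we will use a linear mixed-effect model", whose purpose is "to estimate the treatment effect as the difference in the time-averaged changes from baseline in these outcome measures" over the 12-month follow-up. It names neither a dependent variable nor covariates.

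Section 9.5.2 defines the outcome: "Percent days abstinent from alcohol and drugs will be used as the primary measure of substance use at each assessment time point". It lists baseline and the 1-, 3-, 6-, 9- and 12-month visits, and the schedule in 6.1 shows the TLFB at all of them. The look-back differs between sections. Section 9.6 uses "percent days abstinent from alcohol and drugs during the past 30 days at each assessment time", whereas 9.5.2 has participants recall use since the preceding follow-up.

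Sections 9.5.1 and 9.6 also name t-tests for the secondary outcomes. Nothing says whether the t-test or the mixed model governs.

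**The concern.** Substance use is one of three outcomes in both Secondary Aim 2 and Secondary Aim 3. An analyst who follows 9.6 literally has an instruction to adjust for baseline in one model and none in the other. If the substance-use model is fitted to change scores without the baseline value, two things follow.

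- **Precision.** Subtracting baseline with a coefficient fixed at 1 brings in baseline noise that a fitted coefficient would remove. The penalty is largest when baseline predicts follow-up poorly.
- **Chance imbalance.** Randomisation is stratified by sex, past-year heroin use and veteran status, not by days abstinent. A chance difference in baseline abstinence therefore moves the unadjusted estimate through regression to the mean.

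A modest correlation is plausible here. Participants may enter having started buprenorphine "treatment within the past 6 months", so a 30-day baseline window can fall partly before treatment for a recent starter and wholly on treatment for someone else. The documents do not say how many participants are recent starters, so this is a reason to look at a range and not an estimate.

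**Working it through.** **The plan's own figure.** There is none for this outcome. The only power statement (Section 9.2, above 85% at a hazard ratio of 0.5 with 200 participants) concerns the primary time-to-event outcome. It reproduces at 87.0% by the Schoenfeld formula and has no bearing here.

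**Inputs.**
- Follow-up visits averaged, k: 5 over 12 months and 2 over 3 months (Sections 6.1 and 9.5.2). The substance-use sentence mentions only 12 months, so k = 2 assumes that the same model serves at 3 months.
- Participants followed: 80% of 200 = 160, or about 80 per arm (Section 4).
- Correlation rho: not given. Assumed range 0.3 to 0.86. The upper end borrows the TLFB test-retest reliability in 6.2.2, which is stated as greater than .86. That is an optimistic stand-in for a correlation over months.
- Unit variance and one common correlation between all visits: assumed.

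**Variance per participant.** The mean of k follow-ups has variance (1 + (k−1)·rho)/k.
- Unadjusted change score: add 1 − 2·rho, giving (k+1)(1−rho)/k.
- Baseline as covariate: subtract rho², giving (1−rho)(1+k·rho)/k.
- Ratio, adjusted to unadjusted: (1+k·rho)/(k+1). The variance reduction from adjusting is therefore k(1−rho)/(k+1).

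At rho = 0.5:
- k = 5: 0.60 unadjusted against 0.35 adjusted; reduction 5 × 0.5/6 = 42%.
- k = 2: 0.75 against 0.50; reduction 2 × 0.5/3 = 33%.

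**Effect on power.** Take an effect that has 80% power when adjusted. This is an illustrative anchor, since the plan sets none. The unadjusted power is Φ(2.80·√ratio − 1.96).

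| rho | Reduction, k=5 | SE inflation, k=5 | Unadjusted power, k=5 | Reduction, k=2 | SE inflation, k=2 | Unadjusted power, k=2 |
|---|---|---|---|---|---|---|
| 0.3 | 58% | 1.55 | 44% | 47% | 1.37 | 53% |
| 0.5 | 42% | 1.31 | 57% | 33% | 1.22 | 63% |
| 0.7 | 25% | 1.15 | 68% | 20% | 1.12 | 71% |
| 0.86 | 12% | 1.06 | 75% | 9% | 1.05 | 76% |

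SE inflation is the unadjusted SE divided by the adjusted SE.

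**Check by simulation.** With 5,000 trials, k = 5, rho = 0.6 and 100 per arm, the variance ratio was 0.68 against 0.667 from the formula. Under no treatment effect, both estimators averaged about −0.001, so neither is biased over randomisations. A mixed model with baseline in the response vector and equal baseline means gave 0.67, the same precision as the covariate.

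**Relaxing the common correlation (k = 5).** Let baseline correlate less with follow-up than the follow-ups do with each other. The reduction becomes (1−rho_b)² divided by the change-score variance.
- rho_b 0.3, follow-ups 0.6: 0.49/1.08 = 45%.
- rho_b 0.5, follow-ups 0.7: 0.25/0.76 = 33%.
- rho_b 0.6, follow-ups 0.8: 0.16/0.64 = 25%.

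**Chance imbalance.** Given a baseline difference d, the unadjusted estimate shifts by −(1−rho)·d. With 80 per arm, the standard error of d is √(2/80) = 0.158 SD. An imbalance of that size shifts the estimate by 0.11 SD at rho 0.3, 0.08 SD at 0.5, 0.05 SD at 0.7 and 0.02 SD at 0.86.

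**The case against.** The strongest reply is that 9.6 is silent and excludes nothing. The phrase about time-averaged changes from baseline defines the effect, not the model terms. The pain model uses almost the same phrase and is baseline-adjusted, so the substance-use sentence may be shorthand for the same model. A mixed model with baseline in the response vector and equal baseline means would also fit the wording and lose nothing. This stands: a reader might infer that the plan prescribes an unadjusted analysis, and the documents do not support that. What remains is that one sentence admits analyses of materially different precision, and that the stated covariate list is introduced by a reason specific to pain.

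A reader might also infer a fixed loss, such as a third of the precision. The documents give no correlation, so no single figure can be defended. A one-third reduction in variance also corresponds to a standard error only about 22% larger.

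Nor is this a bias in the usual sense. The shift is conditional on an observed imbalance and averages to zero over randomisations.

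Two further replies are correct and belong in the fix. The linear model applies only if the data are not highly skewed, so it may not be the one used. And the t-tests are named for pain and functioning too, so adding a covariate to one model does not by itself settle which analysis governs.

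**Conclusion.** The point holds as a free improvement to a secondary analysis. The plan states baseline adjustment for pain and functioning and leaves it unstated for substance use, in both the mixed model and the t-test. If the analysis is run without adjustment, it is less precise at every correlation below 1. Under the equal-correlation assumption, the avoidable share of variance runs from 12% to 58% for the 12-month analysis and from 9% to 47% for a 3-month analysis by the same model, as rho falls from 0.86 to 0.3. If baseline correlates less with follow-up than the follow-ups do with each other, the loss is somewhat smaller but does not vanish. These sizes rest on an assumed correlation, equal variances and use of the linear model. The primary outcome and its power are untouched.

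**What to change.** In Section 9.6, after the description of the substance-use model, state that:

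1. The model for percent days abstinent includes baseline percent days abstinent, time in months and treatment group, as the pain model does. Name the dependent variable. Change and level give the same group estimate once baseline is a covariate.
2. Baseline and follow-up use the same 30-day look-back, and 9.5.2 is aligned with this.
3. Any alternative model adopted because the data are skewed also adjusts for baseline.
4. The baseline-adjusted model, not the t-test, is the governing analysis for Secondary Aims 2 and 3.

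The cost is a few lines of text and one degree of freedom. No new data are needed: the TLFB is already scheduled at baseline, and Section 6.2.2 places randomisation after all baseline data collection.

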10. DATA COLLECTION AND QUALITY ASSURANCE

10.1 Data Collection Forms

Data will be collected following consent from the participant (either electronic or verbal for eligibility screening, and written or verbal consent for the RCT). All forms used for data collection throughout the study will be approved by NCCIH, the IRB, and all PIs prior to implementation as data collection or tracking forms. All staff will receive training on the proper use and storage of all data collection forms and source documents. Data may be collected for this study using a variety of modalities, based on availability at the site and patient preference, and include:

- data collected in-person by research staff using standardized paper forms
- data collected in-person by research staff using REDCap survey via tablet (electronic data capture [EDC])
- data collected remotely from the participant via REDCap online survey (electronic data capture [EDC])
- data collected by research staff via telephone, video chat, and/or US postal mail with responses captured by the researcher either via tablet or computer (through a REDCap assisted survey), or via paper/pencil collection

All data collected will only be identified with the participant's unique study identification numbers and will be kept separate from any identifiable information (either in a separate physical location for paper data or in a separate electronic database for electronic data). This participant study identification numbers will appear on all study data forms and materials, rather than the participant's name or other identifiable information. All data will be stored securely at all times during the study and will be stored based on the data safety requirements of the local site. For any sites that do not have specific data storage requirements, the standard data security requirements of the University of Michigan IRBMED will be used, which includes ensuring that any study forms or documents that contain participant's names and other identifying information will be kept separately from study data on password-protected files on a secure server with restricted access and/or in a locked cabinet in a locked room; and only participants' unique ID number will be kept in the database on password protected file. VA participant audio recordings will be stored on a VA protected server behind a VA firewall. VA consent forms and locator forms will be stored within a locked cabinet within a VA secure office space.

Because this is a longitudinal study in which participants will be contacted a number of times and data will be linked, via a crosswalk file containing contact information linking participants' identifiers with their unique study identification number will be stored separately from any participant data on a secure server in a password protected file. No identifiers or crosswalk for VA participants will be stored at UM. Only coded data will be collected, stored and analyzed at UM. All identifying information of VA participants will be stored on the VA network. Access to electronic data files and folders will be restricted to research staff as noted in the local site IRBs.

Throughout the study, participants will be asked to respond to questions using self-report surveys and research administered interviews on topics such as pain level and related conditions, general health and mental well-being and functioning, substance use, and

buprenorphine treatment involvement and satisfaction. All data collection forms will be reviewed by the Coordinating Center PIs (Drs. [name] and [name]), project managers, and data manager/data analyst before implementation. Since some study visits will take place at either local study sites or in the community, data will be collected offsite and will be transported to specified data storage locations with the use of a locked box or brief case and will be kept with study staff at all times.

With participant permission, PPMI and EUC sessions and the qualitative interview (conducted as part of Secondary Aim 4) will be audio-recorded to ensure therapist and research staff fidelity to the session content and for transcription of the qualitative interviews for analysis. PPMI and EUC sessions will be audio-recorded for treatment fidelity, and will take place over the phone or video chat. Participants may choose the video chat platform most convenient for them (e.g., Zoom, BlueJeans, FaceTime or Skype for Business) for sessions and interviews, however, HIPAA compliant platforms (e.g., Zoom) will be recommended and encouraged. Qualitative interviews will take place in-person whenever possible but may also be conducted over the phone or via video chat at the request of the participant. The audio recordings for the PPMI and EUC sessions and qualitative interviews will be done with a digital voice recorder approved for use at local sites as necessary. The audio-recordings of the interviews will be destroyed after the files are uploaded to a password-protected, secure server with restricted access. Participants will be asked not to mention names or other identifying information in during the recorded interview. Any identifying information will be removed from transcriptions.

Paper copies of interview questions and notes may be kept along with the transcript of the qualitative interviews in the participants' research file. All project staff members are responsible for reviewing the data provided by the participant following collection to ensuring the accuracy, completeness, legibility, and timeliness of the data reported. All source documents should be completed in a neat, legible manner to ensure accurate interpretation of data. Once collected, participant data will remain confidential. Only study team members who have completed appropriate training in the protection of human subjects at the VHA and University of Michigan or other local site requirements will have access to the data. Hard copies of data will be stored in a locked data storage room in a University of Michigan secure cabinet. Electronic data will be stored on a secure UM server on password-protected files and coded by subject identification number so that participants cannot be identified by their research record. Any data collected via pen and paper, such as tracking forms, will be manually entered into the study REDCap database using double entry when possible. Data cleaning will be conducted throughout the data collection period to ensure the production of a final dataset for analysis at the end of data collection. Regulatory Binder information may be in the form of both electronic and hard copy files. These binders will be stored in the same manner as study data described above. Physical security of data will be assured by daily and weekly back-ups.

Data quality will be monitored by random inspection of the completed forms by the project managers and/or research associate and any problems detected will be discussed with the PIs. The project managers will also periodically observe research staff completing study activities (such as the informed consent process, study assessments, entry of study data into project databases, documenting study activities, etc.) to assure all procedures are being followed according to the protocol. The project managers may additionally contact

participants following completion of study assessments to ensure that project staff members completed all study tasks and followed procedures during the assessments. Any deviation to the protocol that may have an effect on the safety or rights of the participant or the integrity of the study will be report promptly to the appropriate agencies and boards per our reporting plan, and will result in staff re-training. Quality and delivery of both the PPMI and EUC sessions will be monitored by the PIs, project managers, and/or research staff responsible for providing therapist and research staff supervision. Adherence to therapy techniques will be monitored using audiotapes and individual supervision according to the protocol for the PPMI condition. If PPMI therapy drift is observed, the therapists will be re-trained appropriately. The project managers will also periodically look at eligibility criteria, participant recruitment and retention numbers, and randomization tables to determine they are accurate and up to date. Project managers and other research staff will communicate regularly to monitor study progress.

